10.3 Reporting of SAEs

Following the subject's written consent to participate in the study, all SAEs should be collected and reported, including those thought to be associated with clinical trial procedures. Following study completion, any SAE thought to be related to study drug or clinical trial procedures should also be reported to the sponsor: The Methodist Hospital Research Institute and the local IRB.

SAE terminology and severity grading will be based on (CTCAEv3).

The following categories and definitions of causal relationship to study drug should be considered for use for this clinical study.

- Certain: There is a known causal relationship between the study drug and the SAE. The event responds to withdrawal of study drug (dechallenge), and recurs with rechallenge when clinically feasible. (>95% certainty)
- Probable: There is reasonable causal relationship between the study drug and the SAE. The event responds to dechallenge. Rechallenge is not required. (65%-95% probability)
- Possible: There is reasonable causal relationship between the study drug and the SAE. Dechallenge information is lacking or unclear. (35%-65% probability of relatedness)
- Not likely: There is temporal relationship to study drug administration, but there is not a reasonable causal relationship between the study drug and the SAE. (5-35% probability of relatedness)
- Not related: There is not a temporal relationship to study drug administration (too early, or late, or study drug not taken), or there is known causal

relationship between the SAE and another drug, concurrent disease, or other circumstance. (<5% chance of relatedness)

- Adverse events classified as "serious" require expeditious handling and reporting to the sponsor (TMHRI) and local IRB to comply with regulatory requirements.
- All serious AEs whether related or unrelated to ixabepilone, must be immediately reported to the sponsor (TMHRI) by the investigator or designee within 24 hours of becoming aware of the event. If only limited information is initially available, follow-up reports are required. The original SAE form must be kept on file at the study site.

All SAEs should be faxed or emailed to TMHRI at:

The Methodist Hospital Research Institute [contact]

Email: [contact] and [contact]

For studies conducted under an Investigator IND, any event that is both serious and unexpected must be reported to the FDA as soon as possible and, in no event, later than 7 days (death or life-threatening event) or 15 days (all other SAEs) after the investigator's or institution's initial receipt of the information. The Methodist Hospital Research Institute will be provided with a simultaneous copy via facsimile of all adverse events filed with the FDA. SAEs should be reported on the MedWatch Form 3500A, which can be accessed at:

http://www.accessdata.fda.gov/scripts/MedWatch/

MedWatch forms should be mailed or faxed to the FDA at: MEDWATCH [name]

[name] Fax: [name] ([name])

All SAEs are to be simultaneously be faxed to Bristol-Myers Squibb at:

Global Pharmacovigilance and Epidemiology Bristol-Myers Squibb Company [contact] Email:[contact]

- Collection of complete information concerning SAEs is extremely important. Full descriptions of each event will be followed by the sponsor. Thus, follow-up information which becomes available as the SAE evolves, as well as supporting documentation (e.g., hospital discharge summaries and autopsy reports), should be collected subsequently, if not available at the time of the initial report, and immediately sent using the same procedure as the initial SAE report.
- An overdose is defined as the accidental or intentional ingestion of any dose of a product that is considered both excessive and medically important. For reporting purposes, the sponsor considers an overdose, regardless of adverse outcome, as an important medical event.
- AEs should be followed to resolution or stabilization, and reported as SAEs if they become serious. This also applies to subjects experiencing AEs that cause interruption or discontinuation of ixabepilone, or those experiencing AEs that are present at the end of their participation in the study; such subjects should receive posttreatment follow-up as appropriate.

In BMS supported trials, all SAEs must be collected which occur within 30 days of discontinuation of dosing or completion of the patient's participation in the study if the last scheduled visit occurs at a later time. In addition, the Investigator should notify BMS of any SAE that may occur after this time period which they believe to be certainly, probably or possibly related to ixabepilone. ⁴⁸

CA163-157 Clinical Protocol

11. Data Management

An outcome database would be created for this specific project. Using Excel (spread sheet) program

12. Statistical Design and Analyses

12.1 Sample size estimate

The published study CA163-080 has shown that the pathological complete response (pCR) rate is 18% based on a single agent Ixabepilone data, and is the same percentage that we assume for patients that will be treated with ixabepilone (Treatment Arm 1). With total 108 patients (54 in each arm), we will be able to detect 25% difference in pCR rates between the arm with Ixabelpilone plus Cetuximab (Treatment Arm 2) and Arm 1 with 81.9% power and a two-sided significance level of 0.05. A total of 116 patients will be enrolled to allow for 6.5% dropout before randomization of 108 patients. Table 1 provides power estimates to detect hypothesized 25%, 27%, 29%, and 31% difference in pCR rate in the treatment am 1 compared to the treatment arm 2 with given sample size of 54 patients in each arm.

Projected pathological complete response rate		Estimated power (%)
Treatment Arm 1	Treatment Arm 2	
18%	0.43%	81.9
	0.45%	87.0
	0.47%	91.0
	0.49%	94.0

Table 1. Power to detect different differences of pathological complete response rates in the two arms with given sample size of 54 patients in each arm.

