Ixabepilone BMS-247550 CA163-157 Clinical Protocol

TMHRI IRB#0908-0265 BMS Protocol #: CA163-157

ICE Trial

RANDOMIZED OPEN-LABEL NEO-ADJUVANT PHASE II STUDY COMPARING IXABEPILONE (I) VS IXABEPILONE PLUS CETUXIMAB (IC) IN TRIPLE NEGATIVE BREAST CANCER PATIENTS (ICE)

VERSION: 8.0 DATE: 8/9/2012 PHASE: II IND Number: 104,307

[name]. Director, Methodist Cancer Center The Methodist Hospital/Weill Cornell University [name] [contact] [contact] [contact]

STUDY SUMMARY

Title:	Randomized open-label neo-adjuvant phase II study comparing					
	ixabepilone (I) vs. ixabepilone plus cetuximab (IC) in Triple negative breast					
	cancer patients					
Objectives:	Primary Objective:					
	1. To determine the pathologic complete response rate (pCR) (breast and					
	axilla) of Ixabepilone versus Ixabepilone when combined with cetuximab					
	in patients with invasive breast adenocarcinoma T1N1-N3M0 or					
	T2-4 N0-3M0 disease who are Triple negative and who are candidates for					
	preoperative chemotherapy.					
	Secondary Objective(s):					
	1. To evaluate overall objective response rate in both treatment groups.					
	2. To assess toxicity of each regimen.					
	Exploratory Objectives:					
	1. To correlate the expression of biomarkers such as PTEN, EGFR					
	and EGFR-pathway associated genes (including, but not limited to,					
	TGF- α , CRYAB, NRAS, KRAS, AKT3, PTEN, MEK1 and KRAS					
	amplicon genes) with the objective clinical and pathologic response.					
	2. To potentially explore other gene/protein expression patterns,					
	mutations and gene/chromosomal copy number alterations related					
	to sensitivity or resistance to ixabepilone, other anti-microtubule					
	agents and cetuximab. These additional exploratory analyses may					
	include, but are not limited to, beta tubulin isoforms, ABC					
	transporters, TACC3, HCAPG, GTSE1, Kallikreins and defined					
	gene models associated with ixabepilone response.					

Study	-Patients with either T1N1-N3M0 or T2-4 N0-3M0 disease who are Trip				
population:	on: negative and who are candidates for preoperative chemotherapy.				
Sample	116 patients.				
Size:					
Number of	Single Institution: The Methodist Hospital Research Institute.				
Centers:					
Treatment	This is a randomized open-label phase II trial; 116 triple negative breast				
Plan:	cancer patients will be randomized equally between 1) Ixabepilone or				
	2) Ixabepilone plus Cetuximab.				

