	Uncontrolled chronic viral infections or patients requiring parenteral					
	antibiotics will be excluded. Patients taking highly active anti-viral					
	therapies and with controlled disease will be allowed to participate.					
	Patients with an active, bleeding diathesis or on oral anti-vitamin K					
	medication (except low dose coumarin defined as 1 mg a day)					
	Other concurrent and/or uncontrolled medical disease which could					
	compromise participation in the study (i.e., uncontrolled diabetes,					
	uncontrolled hypertension, severe infection, severe malnutrition,					
	unstable angina, or congestive heart failure - New York Heart					
	Association Class III or IV, ventricular arrhythmias, active ischemic					
heart disease, myocardial infarction within six months, o						
	or renal disease, active upper GI tract ulceration).					
	 Patients with a pre-existing peripheral neuropathy(> grade1). 					
Statistical	Blocked randomization will be used to randomly assign patients either to					
Design:	arm 1 or arm 2. A total of 116 patients will be enrolled to allow for 6.5%					
	dropout before randomization of 108 patients, given sample size of 54					
	patients in each arm to be able to detect 25% difference in pathological					
	complete response rates between the arm with Ixabelpilone plus					
	Cetuximab and the arm with Ixabepilone with 81.9% power and a two-					
	sided significance level of 0.05.					

TMHRI Version: 8

RANDOMIZED OPEN-LABEL NEO-ADJUVANT PHASE II STUDY COMPARING IXABEPILONE (I) VS IXABEPILONE PLUS **CE**TUXIMAB (IC) IN TRIPLE NEGATIVE BREAST CANCER PATIENTS (ICE).

Randomized open-label neo-adjuvant phase II study comparing ixabepilone (I) vs. ixabepilone plus cetuximab (IC) in Triple negative breast cancer patients.

0.0 STUDY SUMMARY	2
0.0 Schema	7
1.0 Synopsis	11
1.1 Primary Objective(s)	11
1.2 Secondary Objective(s)	11
1.3 Exploratory Objective (s)	12
2.0 Study Flow chart or Schedule of Events	14
2.1 Study Procedures by Visit and Treatment Cycle	16
2.2 Screening/Baseline visit	16
2.2.1 Radiological Evaluation Visit	17
2.3 Cycle 1 Clinic Visit	17
2.3.1 Cycle 1 Post-Infusion Laboratory Visits	18

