10.1 Common side effects of Ixabepilone65	
10.2 Common side effects of cetuximab71	1
10.3 Reporting of SAEs73	3
11. Data Management70	6
12. Statistical Design and Analyses70	6

1	I3. Reference/Bibliography	79
	12.3 Interim data analysis	.78
	12.2 Statistical analysis	.77
	12.1 Sample size estimate	.76

1.0 Synopsis:

Ixabepilone and capecitabine combination has demonstrated to be an active regimen in patients with metastatic breast cancer (MBC) after failing an anthracycline and a taxane regimen. Cetuximab is active in tumors that express EGFR with demonstrated activity in head and neck and colorectal tumors. A proportion of breast cancers are known to express EGFR. Cetuximab's mechanism of action suggests the possibility of efficacy in breast cancer patients and several studies show that it may be efficacious in Triple Negative Breast Cancer (TNBC). This study seeks to evaluate Ixabepilone alone or in combination with cetuximab as a possible way to increase antitumor activity.

This is a randomized open-label phase II trial, one hundred sixteen triple negative breast cancer patients will be randomized equally between 1) Ixabepilone or 2) Ixabepilone plus Cetuximab. Randomization will be stratified by disease stage (T1N1-3M0 or T2-4 N0-3M0).

At the baseline all patients will receive a physical assessment, imaging, a blood draw, and a biopsy prior to the start of treatment.

1.1 Primary Objective(s):

To determine the pathologic complete response rate (pCR) (breast and axilla) of Ixabepilone versus Ixabepilone when combined with cetuximab in patients with invasive breast adenocarcinoma T1N1-N3M0 or T2-4 N0-3M0 disease who are Triple negative and who are candidates for preoperative chemotherapy.

1.2 Secondary Objective(s):

To evaluate overall objective response rate in both treatment groups.

To assess safety and toxicity of each regimen.

1.3 Exploratory Objective(s):

To correlate the expression of biomarkers such as PTEN, EGFR and EGFRpathway associated genes (including, but not limited to TGF- α , CRYAB, NRAS, KRAS, AKT3, PTEN, MEK1 and KRAS amplicon genes) with the objective clinical and pathologic response.

For all samples available, the following tests will be conducted:

- Immunohistochemical detection of EGFR, and the PTEN expression in tumor tissue samples. For those EGFR-pathway associated genes (including, but not limited to, TGF-α, CRYAB, NRAS, KRAS, AKT3, PTEN, MEK1 and KRAS amplicon genes) an mRNA-based assay will be used.

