given in a dose of 40 mg/m² as a 3-hour IV infusion every 3 weeks. A total of 161 subjects were treated. Median age was 55 years. Results in evaluable subjects were Primary Best Overall Response Rate (Complete Response [CR] or Partial Response [PR]): 98/161 (61%); Pathologic Complete Response in Breast [pCR_B]: 29/161 (18%); and Pathologic Complete Response in Breast and Lymph Nodes [pCR_{BL}]: 17/161 (11%). Independent assessment of subject responses yielded pCR_B and pCR_{BL} rates of 14% and 9%, respectively. In subjects with ER-negative, ER-/PR-negative, and triple-negative tumors, as assessed by locally read immunohistochemistry (IHC) and fluorescence in situ hybridization (FISH), investigator-assessed pCR_B rates were 29%, 33%, and 26%, respectively. The pCR_{BL} rates were 19%, 23%, and 19%, respectively.

No deaths were reported. Twelve (8%) subjects reported SAEs. Among these subjects, 10 (6%) reported at least 1 SAE assessed as possibly, probably, or certainly related to ixabepilone therapy. These SAEs included peripheral or sensory neuropathy, febrile neutropenia, neutropenia, vomiting, and hypersensitivity, each reported in 2 subjects; and mucositis, constipation, diarrhea, stomatitis, lymphopenia, leukopenia, thrombocytopenia, increased ALT, and increased AST, each reported in 1 subject.

Treatment-related adverse events were reported in 97% of subjects. The most common (\geq 15% of subjects) were alopecia (86%), myalgia (50%), arthralgia (30%), asthenia (27%), neutropenia (21%), peripheral sensory neuropathy (20%), nausea (19%), fatigue (19%), and diarrhea (15%). Most were Grade 1 to 2. Grade 3/4 treatment-related adverse events were reported in 25% of subjects. The most common Grade 3/4 event was neutropenia (14%).¹²

CA163-081: Phase 2 Study in Refractory MBC

CA163-081 was a single-arm, open-label, multicenter, multinational, two-stage design study of ixabepilone in MBC that was resistant to an anthracycline, a taxane, and capecitabine. A total of 126 subjects were treated. Data from this study have been published. Of the 126 treated subjects, 113 were evaluable for response. Subjects were heavily pretreated: 88% had received \geq 2 lines of prior chemotherapy in the metastatic setting. Independent Radiology Facility (IRF)-

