7.0 Treatment Plan/Methods

This is a randomized open-label phase II trial; 116 triple negative breast cancer patients will be randomized equally between 1) Ixabepilone or 2) Ixabepilone plus Cetuximab. The study population will include patients≥ 18 years of age diagnosed with invasive mammary carcinoma. Patients will be assigned to treatment arms using a stratified blocked randomization, with strata based on disease stage (T1N1-3M0 or T2-4 N0-3M0). All patients will receive a physical assessment, imaging, a blood draw, and a core needle biopsy (CNB) a biopsy prior to the start of treatment.

7.1 Treatment Arm 1

Patients will receive Ixabepilone 40mg/m² given over approximately 3-hours on day 1 Patients will receive a total of four cycles of this combination with each cycle given 21(+/- 3) days.

Subjects will be premedicated approximately 1 hour before the ixabepilone infusion with either 1) both an oral H1 blocker (diphenhydramine 50 mg or equivalent) and an oral H2 blocker (e.g., ranitidine 150 300 mg or cimetidine 300–800 mg or nizatidine 150-300 mg or famotidine 20–40 mg); or 2) with premedication per institutional standards. Premedication with steroids is indicated in subjects who developed a hypersensitivity reaction to ixabepilone in previous cycles. Patients with severe reaction should not be retreated (see dose modification chart below).

7.2 Treatment Arm 2

Patients will receive Ixabepilone 40mg/m^2 given over approximately 3-hours on day 1 followed by Cetuximab given on day 1 at 400 mg/m² as an initial loading dose (first infusion) administered as a 120-minute IV infusion (maximum infusion rate 5 mL/min) followed by 250 mg/m² infused over 60 minutes (maximum infusion rate 5 mL/min) as a subsequent weekly dose. Patients will receive a total of 4 cycles of this combination with each cycle being 21 (+/-3) days.

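### The number to be randomised is 108 in two places and 116 in three, which leaves open whether 81.9% power allows for unassessed patients; the 18% control rate comes from a different endpoint and population

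*Combined protocol and SAP*

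**What the plan says.** **Number randomised.** Section 12.1 bases its power on 54 patients per arm: "A total of 116 patients will be enrolled to allow for 6.5% dropout before randomization of 108 patients". The Statistical Design entry of the study summary says the same: "dropout before randomization of 108 patients, given sample size of 54" patients in each arm. Three other places give the larger figure as the number randomised:

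- Study summary, Treatment Plan: "This is a randomized open-label phase II trial; 116 triple negative breast" cancer patients, to be randomised equally.
- Section 1.0: "one hundred sixteen triple negative breast cancer patients will be randomized equally between" the two arms.
- Section 7.0: "116 triple negative breast cancer patients will be randomized equally between" the two arms.

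The summary's Sample Size line gives 116 patients without saying enrolled or randomised, so it fits either version.

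**Control rate.** Section 12.1 says "The published study CA163-080 has shown that the pathological complete response (pCR) rate is 18% based on a single agent Ixabepilone data" and assumes that rate for Arm 1. In section 4.0.2 the 18% belongs to the breast-only line for all treated subjects, which opens "Pathologic Complete Response in Breast [pCR_B]: 29/161 (18". The same paragraph gives 11% (17/161) for breast plus lymph nodes in all subjects. For ER-negative, ER-/PR-negative and triple-negative tumours in turn, it says of breast plus lymph nodes that the "rates were 19%, 23%, and 19%, respectively". The triple-negative figure is therefore 19%. Section 1.1 defines the primary endpoint as pCR in breast and axilla in triple-negative patients.

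**Unassessed patients.** Section 12.2 analyses patients by randomised arm whatever their compliance. It gives no rule for a randomised patient who has no pCR assessment.

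**The concern.** Two totals for one quantity leave the site without a defined point at which to stop randomising. They also change what the stated power means. Loss before randomisation costs no power, because the power calculation starts with the patients who are randomised. Loss after randomisation does cost power. The position of the 6.5% therefore decides whether 81.9% already covers missing assessments.

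The protocol has routes to a missing result. Section 7.4 lets a patient withdraw consent for all procedures, and section 7.3.2 allows radiation as the local therapy in place of surgery. In an open-label trial, the scoring of such patients should be fixed before results are known.

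The control rate is a separate matter. If the 18% describes another endpoint in another population, 12.1 does not justify the assumption it makes, even if the number happens to be close to the right one.

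**Working it through.** **Inputs.** From 12.1: 54 per arm, 18% vs 43%, two-sided 0.05, 6.5% loss. From 4.0.2: 19% (breast plus nodes, triple-negative). From 1.0 and 7.0: 116 randomised, which is 58 per arm.

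**Method.** Exact power of the uncorrected chi-square test is the sum, over all i and j from 0 to n, of Bin(i; n, p1) × Bin(j; n, p2) for those pairs with |i − j|/n ÷ √(2p̄(1 − p̄)/n) > 1.96, where p̄ = (i + j)/(2n).

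**Step 1: reproduce the plan.** With n = 54 and p1 = 0.18:

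| Arm 2 rate | Exact power | Table 1 |
|---|---|---|
| 43% | 81.87% | 81.9 |
| 45% | 87.00% | 87.0 |
| 47% | 91.03% | 91.0 |
| 49% | 94.05% | 94.0 |

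All four rows agree to within rounding. A hand check by the pooled normal approximation for the first row, with p̄ = 0.305: (0.25 − 1.96 × √(2 × 0.305 × 0.695/54)) ÷ √((0.18 × 0.82 + 0.43 × 0.57)/54) = (0.25 − 0.1737)/0.0853 = 0.895, so power is 81.5%. The plan's arithmetic is sound. Table 1 does print the Arm 2 rates as 0.43%, 0.45%, 0.47% and 0.49%, where 43% to 49% is meant.

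**Step 2: 108 or 116.** The plan's inflation is 108/0.935 = 115.5, rounded up to 116. Read the other way, 116 × 0.935 = 108.5, or 54 per arm.

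- 108 randomised, all assessed (54 per arm): 81.9%.
- 116 randomised, all assessed (58 per arm): 84.9%.
- 116 randomised, 6.5% unassessed and excluded (54 per arm analysed): 81.9%.
- 116 randomised, 6.5% unassessed in each arm and counted as non-pCR: the rates become 0.18 × 0.935 = 0.1683 and 0.43 × 0.935 = 0.4021, and power at 58 per arm is 81.4%.

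**Step 3: control rate.**

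- 19% vs 44%, 54 per arm (25-point difference kept): 81.2%.
- 19% vs 43%, 54 per arm (Arm 2 rate kept): 78.2%.
- 19% vs 44%, 116 randomised, 6.5% counted as non-pCR: rates 0.19 × 0.935 = 0.1777 and 0.44 × 0.935 = 0.4114; power at 58 per arm is 80.5%.

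**The case against.** The strongest reply is that the 81.9% may already allow for loss. A reader might infer from 12.1 that the stated power simply assumes every randomised patient is assessed. That holds only if 108 is the number randomised. Under the Treatment Plan, 1.0 and 7.0, 116 are randomised and 54 per arm is what remains after 6.5%. This stands, and it is why the position of the 6.5% has to be settled first.

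A reader might also infer that the wrong source figure leaves the trial underpowered. The documents do not support that: with the planned 25-point difference kept, power falls by 0.7 points. Section 12.1 offers 18% as an assumption, and 19% is itself an investigator-assessed subgroup rate with no denominator. Independent review in CA163-080 gave lower overall rates (14% breast, 9% breast plus nodes), with no triple-negative breakdown. This supports correcting the source description and leaving the design as it is.

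Three further inferences do not hold.

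- Stopping or switching drug is not in itself a lost endpoint, since 2.5, 3.0.3 and 7.4 keep such patients in follow-up and surgery.
- The analysis set is not undefined, since 12.2 points to all randomised patients. What is missing is the score for an unassessed one.
- The near-total category in 8.0.1 does not show a mismatch with CA163-080, because the documents do not give that study's pCR criteria.

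**Conclusion.** The contradiction over the number randomised is real and is in the current text. It is worth 3.0 points of power (81.9% against 84.9%, all patients assessed) and decides whether the stated 81.9% contains any allowance for missing assessments. The control rate is taken from a different endpoint and population. Correcting it gives 81.2%, or 78.2% if the Arm 2 rate is held at 43%, at 54 per arm. The missing scoring rule is a narrow gap, but it affects the primary endpoint.

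The figures rest on the uncorrected chi-square test, which reproduces Table 1. The 81.4% and 80.5% also assume that the plan's 6.5% applies after randomisation and equally in both arms. The documents give no post-randomisation loss rate, so the true loss cannot be derived from them. The plan should be corrected, but the design itself is not undermined.

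**What to change.** **Number randomised.** Use one number in the summary (Sample Size, Treatment Plan, Statistical Design), 1.0, 7.0 and 12.1, and say where the 6.5% falls. The sponsor chooses between:

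- **A.** 116 enrolled and 108 randomised (54 per arm), with 6.5% loss before randomisation; the 81.9% for 18% vs 43% assumes that every randomised patient has a pCR assessment.
- **B.** 116 enrolled and randomised (58 per arm), allowing for 6.5% without a pCR assessment after randomisation; with those patients counted as non-pCR, power for 18% vs 43% is 81.4%. The other power entries in Table 1 would be recomputed on the same basis.

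**Section 12.1.** Describe the 18% as the breast-only, all-subtype rate in CA163-080. Cite 19% as the investigator-assessed rate for breast plus nodes in triple-negative tumours, and state the power for 19% vs 44%: 81.2% under A, or about 80.5% under B with 6.5% counted as non-pCR. Correct the Arm 2 entries in Table 1 to 43%, 45%, 47% and 49%.

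**Section 12.2.** Add: *Randomised patients without a pCR assessment count as non-pCR.*

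**Cost.** Text changes only, and neither option enrols more than 116. B randomises 8 more than 12.1 now states. The stated power becomes slightly less favourable, and scoring unassessed patients as non-pCR lowers the observed pCR rate in any arm that has them.
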